8.2 SAFETY AND OTHER ASSESSMENTS

Unscheduled safety assessments may be performed at any time during the study to assess any perceived safety concerns.

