8.2.7 CLINICAL LABORATORY DATA

As outlined in Table 4, non-fasting samples for serum chemistry, hematology, PT, serum antibodies and urinalysis will be collected at designated study timepoints (refer to Table 1). Blood and urine specimens will be collected using applicable safety precautions and processed according to clinical laboratory instructions.

Table 4. Clinical Laboratory Tests

Hematology	Serum Chemistry	Urinalysis	Additional Tests

 • Hemoglobin • Hematocrit • Leukocyte count (total) • Leukocyte count (differential) • Red blood cell count • Platelet count 	
 • Glucose • Total bilirubin • Alanine aminotransferase • Aspartate aminotransferase • Alkaline phosphatase • Blood urea nitrogen • Pregnancy (WOCBP at Screening) • Potassium • Sodium • Calcium • Carbon Dioxide (Bicarbonate) • Chloride • Creatinine • Total Protein 	
 • Specific gravity • pH • Glucose • Protein • Blood • Bilirubin • Ketones 	
 • Prothrombin time (PT) • Urine Pregnancy (WOCBP only)* • Serum pregnancy test at end of study if urine pregnancy test is positive

* If positive at post-treatment timepoints, confirm by serum pregnancy test

It is the investigator’s responsibility to review the results of all laboratory tests as they become available. For each laboratory test result outside the reference range, the investigator must ascertain if the abnormal lab result is a clinically significant result for that individual subject. Likewise, if laboratory tests are taken at follow-up visits, the investigator must ascertain if this is an abnormal and clinically significant change pretreatment for that individual subject. The investigator may repeat the laboratory test or request additional tests to verify the results of the original laboratory test. The investigator must sign and date all written laboratory results (chemistry, hematology plus PT, and urinalysis) and note Not Clinically Significant (NCS) or Clinically Significant (CS) for each out of range laboratory value. If a laboratory value is determined to be a clinically significant result for that subject, this may be considered an AE. Refer to **Section 8.2** for further information.

[REDACTED]

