6.1. General Methods

- Efficacy endpoints will be summarized by dose and/or treatment cycle, unless otherwise specified.
- Continuous variables will be summarized using the number of observations (n), mean, standard deviation (SD), median, minimum (min), and maximum (max). Categorical variables will be summarized using number of observations (n), frequency and percentages of subjects.
- All relevant subject data will be included in listings. All subjects entered into the database will be included in subject data listings.
- Unless otherwise specified, if a subject has more than one observation at a given time point, the value closest to the target day for that visit will be used. If two observations are equal distance from the target day, the later observation will be used.
- All analyses and outputs will be generated using SAS® version 9.4 or higher.

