9.5. Laboratory Evaluations

[figure not shown]
Non-fasting samples will be collected for serum chemistry, hematology, coagulation (prothrombin time), and urinalysis. In addition, for women of child bearing potential, a serum pregnancy test will be collected. If a urine pregnancy test is positive, a serum pregnancy test will be performed to confirm. The hematology tests that will be collected are: Hemoglobin, Hematocrit, Leukocyte count (total), Leukocyte count (differential), Red blood cell count, and Platelet count. Serum chemistry tests that will be collected are: Glucose, Total bilirubin, Alanine aminotransferase, Aspartate aminotransferase, Alkaline phosphatase, Blood urea nitrogen, Pregnancy (women of childbearing potential at Screening), Potassium, Sodium, Calcium, Carbon dioxide (Bicarbonate), Chloride, Creatinine, Total protein. Urinalysis tests that will be collected are: Specific gravity, pH, Glucose, Protein, Blood, Bilirubin, and Ketones. Other additional tests that will be collected are: Prothrombin time, urine pregnancy for women of childbearing potential, serum pregnancy test at end of study if urine pregnancy test is positive, [REDACTED]. Summary tables and listings will report laboratory results using Système International (SI) units.

This document is confidential.

[figure not shown]
Summary statistics for observed values and changes from baseline will be provided for chemistry, hematology, coagulation, [REDACTED] by dose and treatment cycle for each visit. Summary statistics for observed urinalysis values will be provided by dose and treatment cycle for each visit.

Shift tables will also be provided for shift from Baseline to Week 12 of each treatment cycle and shift from Baseline to Week 52/End of Study. Shift tables will be based on normal ranges and results will be reported as low, normal, or high. For urinalysis values, results will be reported as normal or abnormal. Summaries will be provided by dose and treatment cycle.

A listing will be provided for all laboratory values at all visits. A listing of all out-of-range or clinically significant laboratory test results at any evaluation will be provided. Determination of clinical significance for all out-of-range laboratory values were to be made by each investigator and will be included in the listing.

This document is confidential.

This document is confidential.

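### The one-value-per-visit rule and the fixed-visit shift tables can understate post-injection laboratory abnormalities, so SAP 9.5 should add a worst-value shift per cycle

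*SAP*

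**What the plan says.** SAP 6.1 (General Methods) sets a default for duplicates that is not limited to efficacy: "Unless otherwise specified, if a subject has more than one observation at a given time point", then "the value closest to the target day for that visit will be used". On ties, "If two observations are equal distance from the target day, the later observation will be used".

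Protocol 8.2.7, in its text on out-of-range results, says: "The investigator may repeat the laboratory test or request additional tests to verify the results of the original laboratory test". Protocol 8.3.4.1 adds that clinically significant abnormal results at the final assessment are to be followed until they resolve or stabilise, and it mentions repeat tests for this. Protocol 8.2 says: "Unscheduled safety assessments may be performed at any time during the study to assess any perceived safety concerns".

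SAP 9.5 plans laboratory tables for "shift from Baseline to Week 12 of each treatment cycle and shift from Baseline to Week 52/End of Study", and adds: "Shift tables will be based on normal ranges and results will be reported as low, normal, or high". Urinalysis is classed as normal or abnormal. The visible text gives no laboratory rule for repeats and no shift to a worst value. SAP 9.5 also provides two listings, one of all laboratory values and one of all out-of-range or clinically significant results whenever they occurred.

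For ECG, SAP 9.8 does give a rule: repeats are averaged, and the QTc categories are also counted over any visit after treatment.

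**The concern.** A second laboratory value at a visit will often exist because the first was out of range; normal values give little reason to repeat. A rule that picks between the two by calendar distance then loses post-injection abnormal values more readily than normal ones. Whether an abnormal value survives depends on something unrelated to safety: whether the subject attended before or after the target day.

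There is a second route. Data are assigned to visits by their label (SAP 6.4). An abnormal value found at an unscheduled check, or on a repeat logged as unscheduled, belongs to neither Week 12 nor Week 52/End of Study, so it cannot enter the shift tables at all.

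Long-term safety is a primary objective, and the shift table is the only categorical laboratory summary by dose and cycle in the visible SAP. Listings hold the individual values but give no rates.

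**Working it through.** The plan states no figure to reproduce, so the check applies the SAP 6.1 rule to every possible visit day.

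**Inputs**
- Window for Week 12 and Week 52/EOS: ±6 days (Protocol 8.1.3, Table 3), which gives 13 possible days.
- Rule: nearest to the target day, later on ties (SAP 6.1).
- Assumptions, not in the documents: the original sample falls evenly over the 13 days, and the repeat carries the same visit label.

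**Condition.** Let the original be drawn d days from the target (d = −6 to +6) and the repeat L days later. The repeat is used when |d + L| ≤ |d|. For L > 0 this means d ≤ −L/2. If the original was drawn on or after the target day, a repeat on a later day never replaces it.

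**Displacement by lag**

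| Lag L (days) | Original days d on which the repeat is used | Share of 13 |
|---|---|---|
| 1 or 2 | −6 to −1 | 6/13 = 46% |
| 3 or 4 | −6 to −2 | 5/13 = 38% |
| 5 or 6 | −6 to −3 | 4/13 = 31% |
| 7 | −6 to −4 | 3/13 = 23% |
| 10 | −6, −5 | 2/13 = 15% |
| 12 | −6 | 1/13 = 8% |
| 13 or more | none | 0% |

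**From displacement to loss.** Displacement alters the table only if the repeat falls in a different category. Of N repeated abnormal values, if a share q return to normal and a share f are displaced, the number lost is N × q × f. With N = 20 and q = 0.5 (an assumption):
- lag 1 or 2 days: 20 × 0.5 × 6/13 = 4.6
- lag 7 days: 20 × 0.5 × 3/13 = 2.3

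That is about 2 to 5 of 20. If no repeat normalises (q = 0), the loss is 0. If every repeat does (q = 1), it is 20 × 3/13 = 4.6 to 20 × 6/13 = 9.2.

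**As a share of all abnormal values at the visit.** If a share r are repeated, the relative loss is r × q × f. With q = 0.5:
- r = 0.25, 7-day lag: 0.25 × 0.5 × 3/13 = 3%
- r = 1, lag of 1 or 2 days: 1 × 0.5 × 6/13 = 23%

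The second route, abnormal values under another label, cannot be sized because the documents give no frequency of unscheduled tests. With a worst-value shift in which all samples are eligible, the displaced share is 0% at every lag.

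**The case against.** The strongest reply is that the mechanism depends on things the reader cannot see. SAP 6.1 is only a default, and text is redacted after SAP 6.2, in SAP 6.4 and in SAP 9.5, so an override for laboratory repeats may exist. This stands: one can say that none is visible, not that none exists. A repeat logged as unscheduled also never competes with the Week 12 value. This stands too, but such a repeat is then left out of the shift tables altogether, so a worst-value shift is useful either way.

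Several stronger readings are tempting, and the documents do not support them:

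- *Every displaced value is a lost abnormality.* No. A repeat that confirms the abnormality on the same side of the range leaves the category unchanged.
- *Same-day redraws always remove the original.* A same-day pair is a tie, so the later value would be used in all 13 cases. But a redraw prompted by a result needs that result first. Protocol 4.1 bars treatment on the day of the parent study's final visit because the safety laboratory results are not yet available. A same-day redraw prompted by the result is therefore implausible, and very short lags are doubtful for the same reason.
- *More than half of repeats displace the original.* Counting only repeats that land inside the window gives 50% to 57% (6/12 at a lag of 1 day, 4/7 at 6 days). That drops late repeats, which are the cases where the original survives.
- *The error runs one way only.* SAP 6.2 takes the latest pre-dose value as baseline. A normal repeat that supersedes an abnormal screening value can make a later abnormality look new, which raises the shift count.
- *The primary endpoints are biased.* The two adverse-event endpoints in SAP 4.1 do not use shift tables, and clinically significant laboratory values may be recorded as adverse events. The visible text does not link the immunogenicity endpoint to these tables either.

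Fixed-visit shifts with full listings are a legitimate descriptive choice. They do not, however, show how many subjects had an out-of-range value at any time in a cycle.

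**Conclusion.** The concern holds in a limited form. As far as the visible text goes, the laboratory shift tables can understate post-injection abnormalities by dose and cycle, either because an in-range repeat displaces an abnormal value or because an abnormal value carries another visit label. The effect of displacement is modest: about 2 to 5 of 20 repeated abnormal values for lags of 1 to 7 days, fewer at longer lags and none from 13 days. These figures assume evenly spread visits, repeats under the same label, and half of repeats returning to normal. They apply to visits with a ±6-day window; an End-of-Study visit after early withdrawal has no target day in the visible text and was not sized. The weakness lies in the aggregate laboratory summary. It does not reach the adverse-event endpoints, and no value disappears from the listings. The change is worth making because it is cheap and removes both routes.

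**What to change.** In SAP 9.5, beside the planned Week 12 and Week 52/End of Study shifts, add a shift from baseline to the worst post-injection value in each cycle, by dose and cycle. Make scheduled, repeat and unscheduled laboratory values all eligible. For tests with two-sided ranges, give one table to the lowest value and one to the highest.

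Leave the SAP 6.1 rule in place for other assessments. The by-visit laboratory statistics need not be forced onto the original sample, since a verification repeat may show that sample to be wrong. The documents describe no result-driven repeats for vital signs, so no change is needed there.

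The cost is a short addition to the SAP and minor programming. Some transient or erroneous values will appear in the new tables, so the counts will look slightly less favourable; the planned fixed-visit shifts beside them give the context.

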6.2. Key Definitions

Study day will be assigned as follows:

[figure not shown]
- Before the first study medication dose date, study day = visit date – dose date.
- After the first study medication dose date, study day = visit date – dose date + 1.

The day the study medication is first given is Day 1, and the day before the study medication is first given is considered Day -1.

Unless otherwise specified, baseline value is defined as the last non-missing value before the first study medication administration. Change from baseline is defined as the post-baseline value minus the baseline value (post baseline – baseline). Percent change from baseline is defined as 100 times post-baseline value minus baseline value divided by the baseline value ($100 * (\text{post baseline} - \text{baseline}) / \text{baseline}$).

[figure not shown]
[REDACTED]

This document is confidential.

6.4. Visit Windows

Analyses will be based on the visit designation. Visits are required to be within specified time windows relative to the Day 1 or Baseline visit.

[REDACTED]

This document is confidential.

7. Demographic, Other Baseline Characteristics and Medication

7.1. Subject Disposition and Withdrawals

The number and percentage of subjects screened, enrolled, completed, and discontinued will be summarized along with the reasons for discontinuation and will be summarized. The number of subjects who received treatment in each cycle will be summarized. The number of subjects in each study analysis population will also be presented. Enrollment will be summarized by Rollover and DeNovo. Listings will be provided for disposition data, study populations and reasons for exclusion from the study population, and inclusion/exclusion criteria not met.

The reason for discontinuation will also be summarized by cycle. A summary of the duration of the subject participation in the study will be produced, including the n, mean, SD, median, minimum, and maximum duration in weeks, as well as the number and percentage of subjects in the following categories of duration: <4 weeks, 4 to <12 weeks, 12 to <24 weeks, and 24 to <36 weeks, and 36 weeks or more. If a subject is lost to follow-up, their participation in the study will be calculated based on their date of last visit. Duration of study participation will also be summarized overall, across all cycles using the following categories: < 24 weeks, 24 to < 36 weeks, 36 to < 48 weeks, and 48 weeks or more.

7.2. Demographic and Other Baseline Characteristics

Demographic and baseline characteristics will be summarized for the safety populations overall and by dose in initial treatment cycle. [REDACTED]

7.3. Medical History and Concomitant Diseases

Medical history and concomitant diseases will be coded according to Medical Dictionary for Regulatory Activities (MedDRA) version 22.0 or later. A summary of medical history and concomitant diseases for the safety population by system organ class (SOC) and preferred term (PT) will be presented. Terms in the table will be sorted alphabetically. The summary will be provided overall and by dose in the initial treatment cycle. A listing will also be provided that includes SOC, PT, and verbatim term for each medical history and concomitant disease. The listing will be sorted by subject, SOC, PT, and verbatim term.

7.4. Other Baseline Characteristics

Summaries will also be provided for the safety population for CD history overall and by dose in the initial treatment cycle. [REDACTED]

7.5. Medication

Prior and concomitant medication will be coded using World Health Organization Drug Dictionary (WHODD) version March 2018 or later. Anatomic Therapeutic Chemical (ATC) level 2 and preferred names will be included in all summaries and listings. Summaries will be provided overall and by dose in the initial treatment cycle for prior medication and by dose in each treatment cycle for concomitant

This document is confidential.

medication. Listings will also include verbatim terms. Summary tables will be presented in alphabetical order, and listings will be presented for each subject by earliest start date and then alphabetical order. The listing will indicate if the medication was prior or concomitant. Prior medications for CD will be summarized and listed separately. Summaries will be provided for the safety population.

7.5.1. Prior Medication

Medications that were stopped before the first study medication dose date will be classified as prior. A summary table will be provided for prior medications.

[figure not shown]
7.5.2. Concomitant Medication

Medications that were taken on or after the first study medication dose date will be classified as concomitant. This classification includes medications that were started after the first study medication dose date or medications that began before and continued to be taken after the first study medication dose date.

[figure not shown]
This document is confidential.

8. Efficacy

[figure not shown]
All efficacy analyses will be performed for the safety population. Efficacy endpoints, including responder rates, will be summarized with descriptive statistics by dose and treatment cycle, unless otherwise specified.

[figure not shown]
This document is confidential.

[figure not shown]
This document is confidential.

[figure not shown]
This document is confidential.

[figure not shown]
This document is confidential.

This document is confidential.

This document is confidential.

This document is confidential.

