The sample size for this study is based on a requirement from Regulatory Authorities to collect safety data on approximately 350 subjects treated with DAXI once and long-term safety data on at least 100 adult subjects treated with 3 or 4 continuous treatments of low-dose or high-dose DAXI for injection, with at least 50 subjects treated with the high-dose DAXI for injection for 3 or 4 continuous treatments. [REDACTED]

[REDACTED]

Analysis Populations:

Intent-to-Treat Population:

The intent-to-treat (ITT) population is defined as all subjects who enrolled in the OLS and received at least one dose of study drug.

The ITT population will be analyzed by specific treatment cycle and dose. The ITT analysis set will be used to conduct efficacy analyses.

[REDACTED]

Safety Population:

The safety analysis population consists of all randomized subjects who received at least 1 injection of study drug. Subjects will be grouped by the treatment they receive rather than their treatment assignment. The safety analysis set will be used to conduct safety analyses.

[figure not shown]
Demographic and baseline characteristics will be summarized for the ITT, PP, and safety populations.

[figure not shown]
Phase:
Description of Sites/Facilities
Enrolling Participants:

[figure not shown]
3
Approximately 80 sites in the US, Canada, and Europe will participate in the study.

[Redacted text block containing multiple lines of blacked-out information]

Participant Duration: Up to 55 weeks, including 3 weeks for screening

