5 STUDY POPULATION

5.1 INCLUSION CRITERIA

All participants must meet the following inclusion criteria:

1. Adults, 18 to 80 years of age

[figure not shown]
2. Meets diagnostic criteria for isolated CD (idiopathic; dystonic symptoms localized to the head, neck, shoulder areas) with at least moderate severity at Baseline (Day 1), defined as a TWSTRS-total score of at least 20, with at least 15 on the TWSTRS-Severity subscale, at least 3 on the TWSTRS-Disability subscale, and at least 1 on the TWSTRS-Pain subscale (minimum TWSTRS subscale criteria applicable only to subjects not previously enrolled in Study Protocol 1720302)
3. Subjects who were previously enrolled in Study Protocol 1720302, who completed the study, including:
 - a) Those with no reduction or have an increase from baseline in the average TWSTRS-total score at Weeks 4 and 6 (i.e., no improvement or worsened disease status), and the investigator agreed that there was a need for retreatment based on the subject's symptoms and neurologic examination findings
 - b) Those who benefited from study treatment and complete follow-up study visits up to the time point of when their TWSTRS-total score reached/exceeded their target TWSTRS score
 - c) Those who benefit from study treatment but subsequently experienced significant recurrence of CD symptoms (e.g., pain) during the study before their TWSTRS-total score reached their target TWSTRS score and requested retreatment, which the investigator determined was warranted due based on the subject's symptoms and neurologic examination findings
 - d) Those who completed study visits up to Week 36 and their TWSTRS-total score never reached their target TWSTRS score and they never requested another treatment. The investigator determined that these subjects can be followed in the OLS until their TWSTRS-total score is the same or higher than their target TWSTRS score or until they request retreatment, which the investigator determined is clinically indicated
4. De novo subjects (not previously enrolled in Study Protocol 1720302):
 - a) Naïve to BoNT treatment
 - b) BoNT treatment-experienced; if previously treated with BoNTA, the subject must have demonstrated a clinically meaningful response to the last BoNTA treatment based on the clinical judgment of the investigator
5. Written informed consent including authorization to release health information

[figure not shown]

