9.6 PLANNED ANALYSES

All efficacy endpoints, including responder rates, will be summarized with descriptive statistics by dose and/or treatment cycle, unless otherwise specified.

Discontinuation rate will be summarized by dose and cycle as well as overall. Additionally, the number of weeks on study will be summarized with descriptive statistics.

Duration of effect after each treatment, defined as time (number of weeks) from treatment until loss of 80% of the peak treatment effect (i.e., the average of the change from baseline in the TWSTRS-total score at Weeks 4 and 6)

[figure not shown]
- If a subject has no reduction in the TWSTRS-total score at Week 4 and Week 6, his/her duration of effect will be set to 0. If a subject discontinues or withdraws from the study prior or at Week 6, his/her duration of effect will be set to 0.
- If a subject discontinues or withdraws from the study prior to reaching his/her target TWSTRS score at any visit after Week 6, his/her duration of effect will be censored at the last visit. If a subject rolled over from Study Protocol 1720302 at Week 36 prior to reaching his/her target TWSTRS score, his/her duration will be calculated from the injection date in Study Protocol 1720302 to the time his/her TWSTRS-total score reaches/exceeds the target TWSTRS score.

Kaplan-Meier survival curves will be plotted for each dose level for the time-to-event endpoints. Point estimate of median duration and 2-sided, 95% confidence intervals (CIs), will be generated using the log-rank test. A subject might be counted more than once or in multiple groups due to multiple injections cycle. Exploratory statistical comparisons between subgroups and duration of response evaluation may be performed.

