5.3. Safety Population

The safety population is defined as all subjects who enrolled and received at least 1 dose of study drug. The safety population will be analyzed by treatment dose the subject received rather than the treatment dose selected for the subject by the Investigator. The safety analysis set will be used for all analyses

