9.12. Columbia-Suicide Severity Rating Scale

According to the FDA draft guidance for suicidal ideation and behavior ([FDA Guidance Suicidal Ideation and Behavior](#)), the following C-SSRS outcomes, which have yes/no responses, will be sorted in

This document is confidential.

descending frequency of a yes response and numbered to define the composite endpoints for the C-SSRS below:

- Category 1 – Wish to be dead
- Category 2 – Non-specific active suicidal thoughts
- Category 3 – Active suicidal ideation with any methods (not plan) without intent to act
- Category 4 – Active suicidal ideation with some intent to act without specific plan
- Category 5 – Active suicidal ideation with specific plan and intent

- Category 6 – Preparatory acts or behavior
- Category 7 – Aborted attempt
- Category 8 – Interrupted attempt
- Category 9 – Actual attempt
- Category 10 – Completed suicide
- Category 11 – Self-injurious behavior without suicidal intent

A summary table will be provided for each visit by dose and treatment cycle. The summary table will include the yes/no responses to each question in categories 1 through 11 above. In addition, summaries will include any suicidal ideation (highest category with a yes response for categories 1-5 or none if all responses are no), any suicidal behavior (highest category with a yes response for categories 6-10 or none if all responses are no), and any suicidality (highest category with a yes response for categories 1-10 or none if all responses are no), emergence of suicidal ideation (where yes=no suicidal ideation at baseline, and any suicidal ideation at any visit after treatment and no=none), emergence of suicidal behavior (where yes=no suicidal behavior at baseline and any suicidal behavior after treatment and no=none), and worsening of suicidal ideation (yes if most severe suicidal ideation at any post-treatment visit is more severe than the value at baseline for categories 1-5, no if none).

This document is confidential.

[figure not shown]
10. Changes from Analysis Planned in Protocol

[figure not shown]
Additional analyses have been added to determine the impact of COVID-19 on key efficacy variables.

The intent-to-treat and per protocol populations will not be used. As this is an open-label study, only the safety population analysis will be performed. As this is an open-label study, multiple imputation will also not be performed.

[figure not shown]
This document is confidential.

[figure not shown]

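### Week-36 rollovers never dosed in the OLS fall outside every visible efficacy set, so the carry-over duration that Protocol 9.6 defines for them is biased downward

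*SAP*

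**What the plan says.** Protocol 5.1, inclusion criterion 3d, admits 1720302 subjects who completed visits to Week 36, never reached their target score and never asked for retreatment. It says that "these subjects can be followed in the OLS until their TWSTRS-total score is the same or higher than their target TWSTRS score". Follow-up may also end when the subject asks for another injection and the investigator finds it indicated. They can therefore enter under observation, without an injection.

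Protocol 9.6 has a duration rule for them. It applies in this case: "If a subject rolled over from Study Protocol 1720302 at Week 36 prior to reaching his/her target TWSTRS score". For such a subject, the section goes on to state that "his/her duration will be calculated from the injection date in Study Protocol 1720302 to the time his/her TWSTRS-total score reaches/exceeds the target TWSTRS score". The same section censors at the last visit anyone who leaves after Week 6 before reaching target, and plans Kaplan-Meier curves by dose level.

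The analysis set is fixed in three places in the SAP:
- Section 8: "All efficacy analyses will be performed for the safety population".
- Section 5.3: "The safety population is defined as all subjects who enrolled and received at least 1 dose of study drug". Subjects are grouped by dose received "rather than the treatment dose selected for the subject by the Investigator".
- Section 10: the intent-to-treat and per-protocol sets are dropped and "only the safety population analysis will be performed".

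SAP Section 9 uses the same safety population for all safety analyses. The protocol's intent-to-treat set, in the synopsis, carries the same condition: "all subjects who enrolled in the OLS and received at least one dose of study drug".

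**The concern.** A subject followed undosed under 3d enters the safety population only if an OLS injection is given, and that happens once the effect has worn off to target or the subject asks for retreatment. Membership is thus decided by an event after entry that is closely tied to the outcome being measured. The subjects left out include those still in effect when follow-up stops. Under Protocol 9.6 they would be right-censored at the longest durations.

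Kaplan-Meier handles censored observations that are in the data set. It cannot make up for censored subjects who were removed because they had not yet had the event. The carry-over duration for this group would look shorter than it is, and any dose curve that includes the group would lose part of its upper tail. The same subjects would also be missing from the safety summary tables, although not from the listings.

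**Working it through.** **Membership check**

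| Week-36 (3d) rollover | Dosed in OLS? | In safety population? | Status under Protocol 9.6 |
|---|---|---|---|
| Reaches target, re-dosed | Yes | Yes | Event |
| Re-dosed on request before target | Yes | Yes | No target event; no visible rule |
| Reaches target, not re-dosed | No | No | Event, lost |
| Still short of target when follow-up ends | No | No | Censored, lost |

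The third row can arise if a subject declines re-dosing.

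**Does the dose have to be an OLS dose?** SAP 5.3 does not say so outright. Its contrast with the dose selected by the investigator fits the OLS, not Study 1720302, which SAP 3.4 describes as randomised, double-blind and placebo-controlled. The protocol's intent-to-treat wording ties the dose to OLS enrolment. Protocol 7.2 also recognises subjects who are enrolled but receive no study intervention.

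**Illustration of size.** The plan states no figure to reproduce. The documents give no number of 3d subjects, no residual duration after Week 36 and no length of undosed follow-up, so all inputs here are assumptions:
- Residual time from Week 36 to target is exponential with median *m* = 12, 20 or 30 weeks.
- Undosed follow-up lasts *L* = 40 or 52 weeks.
- All who reach target within *L*, and only they, are dosed.

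Share dropped = 2^(−L/m).

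Retained residual median = −m × log2(1 − 0.5 × (1 − 2^(−L/m))).

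Worked case, m = 20 and L = 40: dropped = 2^(−2) = 0.25. Retained median = −20 × log2(1 − 0.375) = −20 × log2(0.625) = 13.6 weeks. Counted from the 1720302 injection, that is 36 + 13.6 = 49.6 weeks against a true 36 + 20 = 56.

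| True residual median (weeks) | L = 40: dropped | L = 40: retained median (weeks) | L = 52: dropped | L = 52: retained median (weeks) |
|---|---|---|---|---|
| 12 | 10% | 10.4 | 5% | 11.2 |
| 20 | 25% | 13.6 | 16% | 15.6 |
| 30 | 40% | 15.5 | 30% | 18.6 |

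The direction is the same throughout, and the loss is smaller with longer follow-up. Retreatment on request before target would lower the dropped shares.

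**Numbers of subjects.** If 2% to 10% of 350 are Week-36 rollovers and 10% to 50% of those are never dosed, the loss runs from 350 × 0.02 × 0.10 = 0.7 to 350 × 0.10 × 0.50 = 17.5, or about 1 to 18 subjects. Both ranges are assumed.

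**The case against.** **Redaction.** SAP 8.1 and 8.2 are blacked out, and the visible SAP contains no duration endpoint or censoring rule. That this analysis will be run, and in whom, is inferred from Protocol 9.6. A special rule could sit in the redacted text. This stands as a caveat, although the population statements in Sections 8 and 10 are categorical and no visible text makes an exception.

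**Origin.** A reader might infer that the SAP created the gap by dropping the intent-to-treat set. The documents do not support this. That set also required a dose, so the gap predates the SAP and restoring the set would not close it.

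**Who remains.** A reader might also infer that only subjects whose effect ended are kept and that every censored observation is removed. Criterion 3d also allows retreatment on request before target, so some retained subjects have no target event.

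**Size.** No visible text sets a clock for an undosed rollover. The synopsis counts Week 52 from Treatment #1, and the Week-40 limit in Protocol 8.1.3 concerns a further treatment after an earlier one. Both follow-up lengths used above are assumptions. The figures describe the 3d subgroup and not the pooled dose curves. Even if 18 of 350 durations were lost, all beyond the median, the median of the remaining 332 would fall at rank 166, which is the 47.4th percentile of the full set (166/350).

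**Safety data.** These subjects' adverse events are not lost altogether. SAP 5.2, 6.1 and 9.3 put all enrolled subjects and all adverse events in listings, and SAP 7.1 reports population counts and reasons for exclusion. Only the summary tables omit them.

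**Materiality.** The primary endpoints are safety and immunogenicity, and the efficacy analyses are descriptive. This limits the consequence but does not remove the bias in the carry-over duration.

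**Conclusion.** The concern holds on the visible text. Protocol 9.6 defines a duration for Week-36 rollovers, and SAP 5.3, 8 and 10 together exclude those never dosed in the OLS from every visible efficacy set and safety summary table. Inclusion depends on a later event linked to the outcome, so the carry-over duration of the 1720302 injection is biased downward.

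This rests on reading study drug in SAP 5.3 as an OLS dose, and on the redacted SAP 8.1 and 8.2 holding no exception. The direction of the bias is clear, but its size cannot be derived from the documents. Under the stated assumptions the subgroup loses between 5% and 40% of its members. A material shift in the whole-study dose curves is not shown. The point merits a correction because the protocol wrote a rule for exactly these subjects and the remedy is small.

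**What to change.** In SAP 5.3 and Section 8:

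1. Define a set for the carry-over duration made up of all enrolled 3d rollovers, whether or not dosed in the OLS. Analyse it by the 1720302 treatment actually received, with placebo recipients kept apart from the DAXI dose curves.
2. Censor those who do not reach target at their last OLS visit, in line with the existing censoring rule in Protocol 9.6.
3. State how subjects re-dosed on request before target are handled in the analysis. One option is to censor at re-dosing, with a sensitivity analysis that counts re-dosing as an event.
4. Report how many 3d rollovers were never dosed in the OLS, and how long they were followed.
5. Keep the safety population for all OLS-injection cycles. No new adverse-event listing is needed.

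If SAP 8.1 or 8.2 already contains such a rule, align 5.3, 8 and 10 with it. If study drug is meant to include the 1720302 injection, one sentence in 5.3 should say so.

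The cost is SAP wording, one population flag and a footnoted subset. It needs the 1720302 treatment allocations and uses whatever OLS visits these subjects attend. The visible schedules count visits from each treatment, so the visits that apply to undosed subjects should be confirmed.
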